Figure 8. No differential effects of mouthwashes on probing depth between implant and non-implant sites. Both groups showed only slight decreases in probing depth. Note that in control condition (rinse A), probing depth was higher for the implant group at baseline.

Implants and Gingival Index

Implant versus normal oral sites also showed a significant main effect ($F = 79.0$, $df = 1$, $p < 0.001$) indicating more and faster gingival index improvement in test group (Group X) for both implant and non-implant sites. Test group (Group X) implants decreased in gingival index scores by 83% while implants in control group (Group A) decreased by 57%. The non-implant sites for control group (Group A) decreased by 23% and for test group (Group X) by 50%. The rate of change was faster for test group (Group X) implants than for control group (Group A) and faster than test group (Group X) non-implant sites. Test Treatment (rinse X) members' implants decrease in gingival index measured 26% versus 19% for those in control group (Group A).

[figure not shown]
Table 6 indicates a strong and statistically significant difference between implant and non-implant sites between and within groups – over time. Figure 9 illustrates the higher gingivitis index in test group (Group X) and greater and faster decrease of gingivitis in test group (Group X).

Table 6. Summary results of general linear model of gingival index measures.

Tests of Between-Subjects Effects

Gingivitis					
Source	Type III Sum of Squares	df	Mean Square	F	Sig.
Intercept	1207.001	1	1207.001	11073.258	0.000
implant	9.949	1	9.949	91.274	0.000
group	9.177	1	9.177	84.187	0.000
implant * group	8.613	1	8.613	79.021	0.000
Error	11.118	102	0.109		

Figure 9. Significant differential effects of mouthwashes on gingival index at implant sites. Both groups showed significant decreases in plaque, but the test group (Group X) reduced gingival index scores more and at a faster rate. Note the difference in gingival index scores at the beginning of the trial.

Implants and Plaque

Plaque scores (PS) for both implant and non-implant plaque scores were higher in the test group (Group X) (2.99 (0.071)) than in the control group (Group A) (2.35 (0.100)) at the first visit, $t = 5.45$, $df = 55$, $p < 0.001$. As with gingival index, PS decreased more for test group (Group X) patients (-0.799 (0.109)) than for control group (Group A) (-0.156 (0.064)) in both implant and non-implant sites, $t = 5.75$, $df = 55$, $p < 0.001$.

Table 7. Summary table of differential effects of control Treatment (rinse A) and test Treatment (rinse X) across implant status and group assignment. The group by implant interaction is significant, indicating the mouthwashes acted differently on implant versus non-implant sites.

Tests of Between-Subjects Effects						
Plaque						
Source	Type III Sum of Squares	df	Mean Square	F	Sig.	
Intercept	1596.963	1	1596.963	3282.732	0.000	
implant	0.547	1	0.547	1.124	0.292	

group	1.108	1	1.108	2.278	0.134
implant * group	7.532	1	7.532	15.483	0.000
Error	49.62	102	0.486		

Both implant and non-implant sites in the test group (Group X) improved significantly more than control group (Group A), but the implant sites improved significantly more for test group (Group X) (Control group (Group A) slope = -0.151, Test Group (Group X) slope = -0.463, one-analysis of variance $p < 0.001$), a 207% reduction in plaque scores over control group (Group A). Thus, test group (Group X) plaque measures on implant sites improved by 57% more than on non-implant sites. See Figure 10.

[figure not shown]

Figure 10. Significant differential effects of mouthwashes on plaque at implant sites. Both groups showed significant decreases in plaque, but test group (Group X) showed significantly greater decrease when testing the difference in slopes.

Conclusions

There is a clear advantage to using ClōSYS® Ultra Sensitive oral rinse treatment (test rinse X) in terms of plaque and gingival index. In addition, ClōSYS® Ultra Sensitive oral rinse (test rinse X) appeared to have a preferential benefit for implant sites, over both control treatment (placebo rinse A) and over non-implant sites. The ClōSYS® Ultra Sensitive rinse (test rinse X) significantly reduced the plaque index and gingival index as compared to initial measures and those in control group (placebo rinse A) ($p < 0.001$). The observation of higher initial gingivitis scores for the ClōSYS® Ultra Sensitive oral rinse (test rinse X) did not affect the superiority of this test group treatment. In controlling for the inequality at baseline, and analysis of covariance showed the reduction of the plaque score remained significantly better in the ClōSYS® Ultra Sensitive oral rinse group (test rinse X) than for the control group (placebo rinse A) ($p < 0.001$). Also, using pre-post difference scores and slopes of the scores over time showed the treatment effect to be robust to the mismatch of initial levels of gingivitis and plaque ($P < 0.001$ for both).

Both groups improved from the use of mouthwashes, but the ClōSYS® Ultra Sensitive oral rinse (test rinse X) improved more and at a faster rate ($p < 0.001$) compared to the control group (placebo rinse A). There was no apparent effect on periodontitis between the two intervals in which it was measured.

Implant sites were significantly more ($p < 0.001$) and faster ($p < 0.001$) improved in the ClōSYS® Ultra Sensitive oral rinse group (test rinse X) than the other non-implanted teeth and in the control group (placebo rinse A).

Both ClōSYS® Ultra Sensitive oral rinse (test rinse X) and placebo rinse (rinse A) tested are safe to oral tissues and did not show any adverse effects.

Both ClōSYS® Ultra Sensitive oral rinse (test rinse X) and placebo rinse (rinse A) tested are safe to oral tissues and do not have any adverse effects.

Signature Page

[name]

Principal Investigator

[name] [name], PhD

REFERENCES

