Samples for microbiome analysis were collected at baseline (Visit 1), Day 14 (Visit 2), and Day 90 (Visit 4). Before collecting samples, each patient was asked to rinse with plain water prior and rest for 5 minutes. Sample collection was performed by gently wiping the buccal and tongue mucosa separately 10 times with three different cotton swabs. Samples were allowed to air dry at room temperature and individually placed in labeled containers with the patient's unique sequential subject identification number and day of collection. These samples were stored in a secure location at -20°C until utilized for microbiome analyses.

[4] Study Design Table

Protocol Study Design and Schedule of Assessments

Evaluation	Screening (0-2wks to Baseline)	Baseline (Visit 1) Day 0	Visit 2 Day 14 (± 3 d)	Visit 3 Day 45 (± 7 d)	Visit 4 Day 90 (± 7 d)
Informed Consent	x				
Inclusion / Exclusion	x	x			
Demographics	x				
Pregnancy Test		x			x
Medical History / Update	x	x	x		x
Medications / Update	x	x	x		x
Periodontal History	x		x		x
Oral Examination	x	x	x		x
Collect Specimen w Swab		x	x		x
Modified Gingival Index / MGI		x	x		x
Bleeding On Probing / BOP	x				x
Probing depth	x	x			x
Turesky modification Plaque Index		x	x		x
Scaling	x				
Eligibility	x				
X-rays		x			x
Enrollment / Randomization		x			
Dispense oral hygiene kit / Diary		x			
Schedule next appt	x	x	x		
Collect residual oral hygiene kit with Diary and distribute oral hygiene kit with Diary for next phase			x	x	
Collect residual oral hygiene kit / Diary					x

[5] Protocol Synopsis

1. Study Title: The Efficacy and Safety of stabilized chlorine dioxide mouth rinse in Therapy of Peri-implant mucositis
2. Study Design: Single Center, randomized, double blind masking, parallel, two-arm clinical study.
3. Objective: The purpose of this study was to analyze efficacy of stabilized chlorine dioxide as a chemical adjuvant for treatment of peri-implant mucositis in a non-surgical treatment protocol with a 3-month follow-up.
4. Study Treatments: 1) Stabilized chlorine dioxide (associated with periodontal basic therapy); and 2) control (placebo associated with periodontal basic therapy).
5. Number of Patients: A total of 54 patients in one clinical site at Stony Brook were randomized, 27 patients received 1) Stabilized chlorine dioxide (associated with periodontal basic therapy); and 27 patients received 2) control (placebo associated with periodontal basic therapy).

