Once a subject had been screened and qualified for study participation, that subject was enrolled and assigned the next available randomization number. The study randomization table was generated by a third-party statistician. This procedure was used to keep the Study Statistician blinded to subject treatments prior to database lock.

WITHDRAWAL

Subjects enrolled in the study were able to elect to withdraw at any time for any reason. Additionally, subjects were able to have been withdrawn from the study at the request of the Principal Investigator for the following reasons:

1. An adverse event required discontinuation of the study rinse in the judgment of the Principal Investigator or designee
2. Subject refused or failed to comply with the study protocol

3. There was a protocol violation(s) or deviation(s) that compromised the use of the subject's data

All patients withdrawn from the study by request or by the Principal Investigator were to be seen, if they consented, for a close-out evaluation. The reason for withdrawal would be recorded by the Principal Investigator or designee on the End of Study form. Patients who experienced complications and discontinued the study on their own were to be scheduled, if they consented, for an immediate follow-up/close-out examination to determine whether an adverse event was present, and if so, the causation of the adverse event was to be recorded. If treatment was needed for any adverse event causing withdrawal, the subject would be monitored until there was a return to normal conditions. (Every effort would be made to follow up with subjects who withdrew from the study.)

Test Product: ClōSYS® Ultra Sensitive Rinse

Placebo: Oral rinse comprising same ingredients as in test product except for stabilized chlorine dioxide.

Materials:

Sponsor shipped prelabelled 'Oral Rinse A' and 'Oral Rinse X' products to the Test Site. Both products were in 16 oz. size bottle and identical in appearance.

Each subject received the following supplies at Baseline (Visit 1) i.e. supplies for 0-14 days:

- a. 1 bottle (16oz) of either Oral Rinse A or Oral Rinse X))
- b. 35 measuring cups
- c. 1 tube of Crest Cavity Protection Toothpaste, Regular (8.2oz) and
- d. 1 ClōSYS toothbrush

Each subject received the following supplies at Visit 2 i.e. supplies for 15-45 days:

- a. 2 bottles (16oz) of either Oral Rinse A or Oral Rinse X)
- b. 70 measuring cups
- c. 2 tube of Crest Cavity Protection Toothpaste, Regular (8.2oz) and

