The patients' data on the three measures were recorded within the Excel Workbooks under three tabs representing the first, second, and third clinical observation periods. So each tab recorded three measures. The first and last tabs recorded probing depth, gingival index, and plaque. The second visit included only gingival index and plaque. Each patient had an individual Excel Workbook. Data were sorted into analysis format through two Excel macros that created a single master data for global scores and a single one for implant and non-implant scores. Data files were saved in comma separated value (csv) format in both wide and long formats for R and SPSS data management, inspection, cleaning, and analyses.

Since many individual variable distributions varied substantially from normal, a gamma log-link function was applied to reduce bias in most statistical tests.

Label Key and Lot #s for Peri-Implant Mucositis Study with Stony Brook University

Rowpar Pharmaceuticals, Inc., released the test material label codes after completion of the clinical study and statistical analysis of the data. The products were labelled as follows:

Study Number: SBU-RPR-Peri-Implant Mucositis-2018

Oral Rinse A: ClōSYS Placebo Oral Rinse, Lot #: 2-80516

Oral Rinse X: ClōSYS® Ultra Sensitive (Unflavored) Oral Rinse, Lot #: 8122A 14-80430

Results

Patients

Fifty-two percent (29/56) of patients in both groups had only one implant. Patients in the control group (Group A) had a total of 47 implants: 11 patients had just one implant, 13 had 2, 2 had 3, and 1 had 4 implants. In the test group (Group X), there were 42 total implants in 26 patients: 18 had 1 implant, 9 had 2, and 2 had 3 implants (see Figure 1). Table 1 gives average values (and standard error of the mean) of Gingivitis Index, Plaque score, and Probing depth at baseline.

Figure 1. Bar chart of numbers of implants per person in control group (Group A) and test group (Group X).

[figure not shown]

Table 1. Patient dental measures at baseline.

		n of patients	n of implants	Modified Gingivitis Index (MGI) (sem)	Plaque score (PS) (sem)	Probing Depth mean (sem)
Control Group (Group A)	implants	27	47	2.06 (0.048)	2.77 (0.115)	3.40 (0.109)

	non-implanted teeth			1.87 (0.039)	2.32 (0.101)	2.72 (0.099)
Test Group (Group X)	implants	26	39	2.82 (0.049)	2.84 (0.057)	2.447 (0.080)
	non-implanted teeth			2.01 (0.028)	2.99 (0.078)	2.65 (0.079)

Global Score Analyses

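### Withdrawal for non-compliance or unusable data, with no as-randomised analysis set or missing-data rule, may bias the comparison, and the conflicting patient counts cannot rule this out

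*Combined protocol and SAP*

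**What the plan says.** The Withdrawal text in section [8] gives three reasons for which the principal investigator may withdraw a subject from the study. The first is tied to an adverse event. The second is "Subject refused or failed to comply with the study protocol" and the third is "There was a protocol violation(s) or deviation(s) that compromised the use of the subject's data". No criteria, timing or blinded adjudication are given for the second and third.

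Withdrawn patients "were to be seen, if they consented, for a close-out evaluation", with the reason entered on the End of Study form. The same paragraph promises every effort to follow up those who withdrew. It does not ask for the Day 14 or Day 90 indices from them.

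The synopsis in [5] describes a "Single Center, randomized, double blind masking, parallel, two-arm clinical study" and states: "A total of 54 patients in one clinical site at Stony Brook were randomized, 27 patients received 1) Stabilized chlorine dioxide"; the other 27 received placebo. Section [11] names a repeated-measures analysis of variance but defines no as-randomised or per-protocol set and no rule for missing visits. The Results report no withdrawals by arm or reason.

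**The concern.** Compliance and protocol deviations are observed after randomisation. In this trial compliance was tracked by rinse weight and diary at Visits 2 to 4, and taste or tolerability of the assigned product can influence it. If patients leave because of such behaviour and their later indices are not collected, the remaining arms are no longer the randomised arms. The third reason goes further, because it is worded as a judgement on whether a patient's data are usable.

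An analysis set of all randomised patients and a stated missing-data rule would limit the damage, but the document has neither. At stake are the primary MGI comparison and the implant-site analyses, which address the disease under study. In a trial of 54 patients, the handling of a few can matter.

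**Working it through.** **1. Counts in the Results text.** The document gives "Fifty-two percent (29/56) of patients in both groups had only one implant". For control, "Patients in the control group (Group A) had a total of 47 implants: 11 patients had just one implant, 13 had 2, 2 had 3"; the remaining patient had 4: 11 + 13 + 2 + 1 = 27 patients and 11 + 26 + 6 + 4 = 47 implants, as stated. For test, "there were 42 total implants in 26 patients: 18 had 1 implant, 9 had 2, and 2 had 3 implants": 18 + 9 + 2 = 29 patients and 18 + 18 + 6 = 42 implants. The 42 implants are reproduced; the stated 26 patients are not. The total of 56 follows from 27 + 29, and 29/56 = 51.8% agrees with the text. Table 1 lists 27 and 26 patients, with 39 test implants.

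**2. Counts implied by the error degrees of freedom.**

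- Table 2 (two groups): 55 + 2 = 57, matching N = 57 in Table 3.
- Table 4 (8 cells, 4 rows per patient): (204 + 8)/4 = 53.
- Tables 5 to 7 (4 cells, 2 rows per patient): (102 + 4)/2 = 53 = 27 + 26.
- The plaque t tests under Implants and Plaque report df = 55, that is 57 patients, so the implant section is not uniform either.

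**3. Arm split of the 57.** From baseline plaque (2.35 control, 3.00 test, 2.67895 overall), n for control = 57 × (2.67895 − 3.00)/(2.35 − 3.00) = 28.15. Allowing for rounding, only 28 fits, which leaves 29 in test. Both exceed the 27 stated as randomised to each arm.

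**4. Possible loss patterns, control v test (Fisher's exact test).**

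| Reading | Control | Test | p |
|---|---|---|---|
| 27/27 randomised to 27/26 in Table 1 | 0 of 27 | 1 of 27 | 1.00 |
| Implant breakdown to Table 1 | 0 of 27 | 3 of 29 | 0.24 |
| Global set (28/29) to implant set | 1 of 28 | 3 of 29 | 0.61 |

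The direction is the same each time, but the difference is 1 to 3 patients and none is conclusive.

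**5. Zeros in Table 3.** Global probing depth at the last visit has a minimum of 0, against 2.04 at baseline, and its SD rises from 0.432843 to 0.804056. MGI and plaque also have minima of 0 at the second and third assessments. A mean over all teeth of exactly 0 for probing depth is hard to read as a measurement.

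Suppose k of n patients are scored 0 and the rest keep the baseline SD s. With p = k/n and m = mean/(1 − p), SD² = (1 − p)s² + p(1 − p)m². For k = 4, n = 57 and mean 2.50351: p = 0.0702, m = 2.692, and SD = √(0.174 + 0.473) = 0.805, against 0.804 reported. By arm, one zero in control gives 0.698 (reported 0.130 × √28 = 0.688) and three in test give 0.883 (reported 0.166 × √29 = 0.894).

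The steepest slopes also fit a last score of 0. Doubling −1.47, −0.99 and −1.53 implies baselines of 2.94, 1.98 and 3.06, all inside the baseline ranges.

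This is an inference from summary statistics. It suggests that the four patients missing from the 53 may have been kept in the global analyses as zeros.

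**The case against.** The strongest reply is that the clause may never have been used. No withdrawal under the second or third reason is reported, and the text does not say that withdrawn patients' data are dropped, although the third reason's wording points that way. The rinses were identical in appearance, and the label codes were released only after the statistical analysis. The follow-up promise also goes beyond a single close-out visit. All of this stands, and it makes the matter a risk, not a demonstrated bias. It does not remove the risk. Behaviour can differ by product without anyone knowing the code, each arm shared one fixed letter, and follow-up in general is not a requirement to collect the Day 90 indices.

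A reader might infer from 29 and 26 that the test arm lost three patients while control lost none. The documents do not support this. Both figures come from one self-contradictory sentence, 29 exceeds the 27 randomised to test, and Table 1 is a baseline table in which later withdrawals would normally still be counted.

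A reader might also try to size the bias by moving from 57 to 53 patients. Back-solving Tables 2 and 3 with an assumed 28/29 split gives a test-arm MGI reduction of about 33%, which rescaling by 29/26 turns into about 25%. That calculation conflicts with the 27.3% stated under Global Gingival Index Score and requires three test patients scored 0 at the last visit. It would describe lost patients retained as zeros, not non-compliers excluded, so it does not measure the effect of this clause.

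**Conclusion.** The concern holds as a weakness of the plan. The investigator may remove randomised patients on post-randomisation grounds, outcome collection after removal is not required, and no as-randomised analysis set or missing-data rule protects the comparison. The clause may therefore bias the result.

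That it did so is not shown, and neither is uneven loss. The size of any bias cannot be computed from the documents. What is established is that 53, 54, 56 and 57 cannot all describe one trial population without explanation. Section [7] says enrolment was complete once the 54 were randomised, so later recruitment does not explain 56 or 57. Until the counts are reconciled, selective loss cannot be ruled out.

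The 53 rests on reading the error degrees of freedom as rows minus cells. The zero-score reading assumes that the non-zero patients kept their baseline spread, and it needs patient-level confirmation.

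**What to change.** **In the plan.** Make the second and third reasons grounds for recording a deviation, not for removal from follow-up or analysis. Collect Day 14 and Day 90 indices from every randomised patient who still consents. Make the primary analysis all randomised patients by assigned arm on verified observed visits, for example with a mixed model, and state its missing-at-random assumption. Keep per-protocol as sensitivity only. This concerns data collection and analysis; it leaves decisions on stopping the rinse untouched.

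**For the completed trial.** Visits that were not made cannot be recovered, but three things can be done:

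- List every withdrawal by arm, date and reason from the End of Study forms.
- Reconcile 53, 54, 56 and 57, and the 29 against 26 in the test arm.
- Check against the patient workbooks whether the scores of 0 in Table 3 are missing visits, and only then re-analyse.

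**Cost.** Wording changes, some dilution of the effect from non-compliers, which is the accepted price of an as-randomised analysis, and modest re-analysis work. A patient who refuses further visits may still be lost, so the missing-data rule is needed in any case.
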